5. INTRODUCTION

Vimseltinib (DCC-3014) is an oral, small molecule, selective inhibitor of colony-stimulating factor 1 receptor (CSF1R) developed by the Sponsor using its proprietary switch control kinase inhibitor technology platform. CSF1R is a tyrosine kinase receptor expressed predominantly on monocytes and macrophages. Vimseltinib binds to the pocket controlling the conformation of the CSF1R kinase domain and locks the kinase domain in the inactive form. In vitro studies have demonstrated vimseltinib to be a potent and selective inhibitor of CSF1R kinase. Vimseltinib is currently being evaluated for the treatment of advanced solid tumors and tenosynovial giant cell tumor (TGCT) in an ongoing Phase 1/2 clinical development study (Study DCC-3014-01-001; NCT03069469).

5.1. Study Rationale

TGCT is a rare tumor arising from the synovium of joints, bursae, and tendon sheaths. Translocation of the colony-stimulating factor 1 (CSF1) gene has been identified in TGCT patients, resulting in overproduction of CSF1 and recruitment of CSF1R-positive inflammatory cells in the affected joint. While surgery is considered the first treatment option, patients may present with tumors that are considered inoperable or difficult to operate on without subsequent morbidity. In addition, local relapse rates of up to 50% have been reported for diffuse-type TGCT patients, requiring multiple surgeries that can lead to substantial damage to the affected joint and impair quality of life. Vimseltinib is expected to have anti-tumor effects by blocking recruitment of CSF1R-dependent tumor-associated macrophages (TAMs) into the tumor microenvironment. Pexidartinib (Turalio[®], 2019), a kinase inhibitor of CSF1R, KIT, and FLT3 was approved by the U.S. Food and Drug Administration (FDA) for systemic treatment of symptomatic TGCT not amenable to improvement with surgery. Pexidartinib is not approved in any other regions and there is currently no approved systemic therapy for symptomatic TGCT outside of the United States. Pexidartinib can cause serious and potentially fatal liver injury and its use requires frequent liver tests for monitoring of liver toxicity. In addition, cognitive impairment may be associated with pexidartinib treatment. Thus, an unmet need remains for a more selective CSF1R inhibitor with an improved safety profile.

5.2. Risk-benefit Assessment

Patients diagnosed with malignant solid tumors or TGCT have enrolled in Phase 1/2 Study DCC-3014-01-001. As of 09 Nov 2021, approximately 54% of patients experienced adverse events (AEs) of Grade 3 or higher. Treatment-emergent AEs of Grade 3 or higher reported in more than 1 TGCT patient were blood creatine phosphokinase (CPK) increased 29 (33.3%), aspartate aminotransferase (AST) increased 4 (4.6%), hypertension 4 (4.6%), lipase increased 3 (3.4%), and amylase increased 3 (3.4%). Observed elevations in transaminase were not associated with symptoms and were not accompanied by bilirubin elevations and/or other signs of liver damage. Safety laboratory values, cardiac function, and clinical signs and symptoms will be monitored throughout the study. Dosing modification guidelines are included in the protocol for AE monitoring (see Section 9.6). Please refer to the Investigator's Brochure (IB) for currently available clinical safety data.

Effects on embryo-fetal development were studied in rats, and vimseltinib was determined **CC** Participants in this study are advised to avoid pregnancy and are required to use highly effective contraception during the study and for 60 days following the last dose of study treatment for females and 120 days for males. Additional details on the available nonclinical toxicology data and clinical safety data are provided in the IB.

Among efficacy evaluable TGCT patients, objective responses were observed as measured by Response Evaluation Criteria in Solid Tumors (RECIST) v1.1 by independent radiological review (IRR) that were sustainable over time. Updated anti-tumor activity data as of 07 Jun 2021 demonstrated an objective response rate (ORR) of 50% in 32 patients across 3 dose escalation cohorts, and an ORR of 42% (all partial response [PR]) in 19 patients in expansion Cohort A at the recommended Phase 2 dose (RP2D), which is also the selected Phase 3 dose. Objective responses were generally achieved after at least 2 cycles of treatment and responses were durable.

The clinical experience continues to support further study of vimseltinib in the TGCT patient population. The risk to participants appears acceptable, and the benefit-risk balance of vimseltinib treatment in TGCT patients for the Phase 3 study is considered positive.

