2. SYNOPSIS

Name of Sponsor: Deciphera Pharmaceuticals, LLC

Name of Active Ingredient: Vimseltinib (DCC-3014)

Title: A Phase 3, Randomized, Placebo-controlled, Double-blind Study of Vimseltinib to Assess the Efficacy and Safety in Patients with Tenosynovial Giant Cell Tumor (MOTION)

Phase of Development: 3

Planned Number of Study Sites: Approximately 45 centers globally

Planned Number of Participants: Approximately 120 participants

Primary Objective:

• To evaluate anti-tumor activity of vimseltinib using Response Evaluation Criteria in Solid Tumors (RECIST) v1.1 by blinded independent radiological review (IRR)

Secondary Objectives:

- To assess anti-tumor activity of vimseltinib using tumor volume score (TVS) and modified RECIST (mRECIST) by blinded IRR
- To assess the effects of vimseltinib on range of motion (ROM)
- To assess the effects of vimseltinib on physical function, worst stiffness, worst pain, and quality of life (QoL) using patient-reported outcome (PRO) measures
- To assess safety and tolerability of vimseltinib

Exploratory objectives are listed in Section 6.1.

Primary Endpoint:

• Objective response rate (ORR, including complete response [CR] and partial response [PR]) per RECIST v1.1 at Week 25

Key Secondary Endpoints:

- ORR per TVS at Week 25
- Change from baseline in active ROM of the affected joint, relative to a reference standard, at Week 25
- Change from baseline in the Patient-reported Outcomes Measurement Information System (PROMIS) Physical Function score at Week 25
- Change from baseline in the Worst Stiffness numeric rating scale (NRS) score at Week 25
- Change from baseline in EQ-VAS (EuroQol Visual Analogue Scale) at Week 25
- Response of at least a 30% improvement in the mean Brief Pain Inventory (BPI) Worst Pain NRS score without a 30% or greater increase in narcotic analgesic use at Week 25

Other Secondary Endpoints:

• ORR per RECIST v1.1

- ORR assessed by mRECIST at Week 25
- Duration of response (DOR; time from first PR or CR to disease progression or death) assessed using RECIST v1.1, TVS, and mRECIST
- Incidence of treatment-emergent adverse events (TEAEs), treatment-emergent serious adverse events, related TEAEs, dose reductions, dose interruptions, and discontinuation of study drug due to adverse event
- Changes from baseline in laboratory parameters, electrocardiograms (ECGs), and vital signs

Exploratory endpoints are listed in Section 6.2.

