Sample Size Justification: The study will randomize approximately 120 patients with TGCT in a 2:1 ratio (vimseltinib:placebo) and will have 98% power to detect a statistically significant difference assuming true ORRs of 35% and 5% in the vimseltinib arm and the placebo arm, respectively, using a two-sided Fisher's exact test at 5% level. Sample size selection is based on considerations for powering the analyses of the primary and secondary endpoints.

[figure not shown]

Figure 1: Study Schema

Patient population:

[figure not shown]
- · Histologically confirmed, symptomatic tenosynovial giant cell tumors
- · Surgical resection will potentially cause worsening functional limitations or severe morbidity
- No prior use of systemic therapy targeting CSF1 or CSF1R (except imatinib and nilotinib)

Abbreviations: biw=twice weekly; CSF1=colony-stimulating factor 1; CSF1R=colony-stimulating factor 1 receptor; MRI=magnetic resonance imaging; PRO=patient-reported outcome; ROM=range of motion.

^a Disease follow-up will be performed for up to 2 years.

Note: Participants will be eligible to receive study drug until radiological confirmation of disease progression (refer to Section 10.5), unacceptable toxicity, withdrawal by participant, physician's decision, or commercial availability of vimseltinib and for as long as vimseltinib is being developed to support the indication, and continuation of treatment does not conflict with the Sponsor's right to terminate the study.

Abbreviations: EOT=End-of-Treatment; PBO=placebo.

Table 1: Schedule of Assessments for Part 1 (Double-blind)

Assessments	Screening	I	Part 1 Do	ouble-bli	nd	EOT ^a	Safety		'ollow-up ^c
		C1		C2 to C6	End of Part 1 Visit (Blinded) ^d		Follow- up ^b	last dose	ears after of study ug)
	D-42 to D-1	D1	D15 (±1d)	D1 (±7d)	D1 (±7d)	w/in +7d of	30 days (±5d)	12 weeks (±4w)	Phone contact
		W1	W3	W5 to W24	W25	decision to stop drug	after last dose	after last dose	every 16 weeks (±4w) thereafter
Informed consent	Х								
Inclusion/exclusion criteria	Х								
Assessment of pain and stiffness symptoms	Х								
Demographics/medical history	Х								
Confirmation of TGCT diagnosis ^e	Х								
Serology testing (hepatitis B/C by central laboratory)	х								
Surgical assessment questionnaire ^f	Х					х	Х	Х	Х
Randomization ^g		Х							
Pregnancy test ^h	Х	Х		Х	Х	х	Х		
PE	Х				Х				
Symptom-directed PE		Х	Х	Х		х	Х		
Height (screening only), vital signs and weight ⁱ	Х	х	Х	Х	Х	Х	Х		

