12-lead ECG (local) ^j	Х	Х	х	х	х	As clin indic			
Clinical laboratory tests ^k									

Deciphera Pharmaceuticals, LLC Vimseltinib (DCC-3014)

Assessments	Screening	P	Part 1 Do	ouble-bli	nd	EOT ^a	Safety		ollow-up ^c
		C1 C2 to End of C6 Part 1 Visit (Blinded) ^d			Follow- up ^b	last dose	ears after of study ug)		
	D-42 to D-1	D1	D15 (±1d)	D1 (±7d)	D1 (±7d)	w/in +7d of	30 days (±5d)	12 weeks (±4w)	Phone contact
		W1	W3	W5 to W24	W25	decision to stop drug	after last dose	after last dose	every 16 weeks (±4w) thereafter
Hematology (central laboratory)	Х	X ^k	Х	Х	Х	Х	Х		
Serum chemistry (central laboratory)	Х	X ^k	Х	Х	Х	Х	х		
Coagulation (central laboratory)	Х			Х	Х	Х			
Urinalysis (local)	Х			Х	Х	Х	Х		
Prior/concomitant medications or procedures	3	0 days prior	to first d	lose throu	ıgh Safety Fol	low-up			
AE reporting	Continuou	1s from signi	ing infor	med cons	ent through S	afety Follo	w-up		
Dosing ¹		Oral dosi thr	ng from ough C6						
PK sampling ^m		Х	Х	X ^m		Х			
Pharmacodynamic sampling ⁿ		Х	Х	X ⁿ		X ⁿ			
Tumor tissue ^o	Х								
Pharmacogenomics	X (Predose)								
Imaging and response assessment ^p	X ^p			C4 only	X ^p	X ^p		X ^p	
ROM assessment ^q	Х			C4 only	х	Xq			
Investigator questionnaires (CGIC/CGIS) ^r		Х	Х	Х	Х	Х			

Deciphera Pharmaceuticals, LLC Vimseltinib (DCC-3014)

Assessments	Screening	F	Part 1 De	ouble-bli	nd	EOT ^a	Safety		ollow-up ^c
		C1		C2 to C6	End of Part 1 Visit (Blinded) ^d		Follow- up ^b	last dose	ears after of study ug)
	D-42 to D-1	D1	D15 (±1d)	D1 (±7d)	D1 (±7d)	w/in +7d of	30 days (±5d)	12 weeks (±4w)	Phone contact
		W1	W3	W5 to W24	W25	decision to stop drug	after last dose	after last dose	every 16 weeks (±4w) thereafter
Patient questionnaires ^s	Х		X	Х	Х	Х			
End of Part 1 interview ^t				Х					
TGCT therapy/surgery after treatment discontinuation						х	х	Х	х
Review of patient dosing diary ^u		Review	Reviewed at every clinic visit through End o Part 1 visit or EOT						
Narcotic analgesic use ^v		ng the same 2 consecutive weeks PROs are collected eening, then C1D1 through End of Part 1 or EOT							
Photographic image of the affected joint ^w (optional)	х	To be perf		nytime po visual ch	ostbaseline if s ange	ignificant			

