Abbreviations: AE=adverse event; C=Cycle; CGIC=clinician global impression of change; CGIS=clinician global impression of severity; D/d=(D)day(s); ECG=electrocardiogram; EOT=End-of-Treatment; MRI=magnetic resonance imaging; PE=physical examination; PF=Physical Function; PK=pharmacokinetics; ROM=range of motion; SAE=serious adverse event; TGCT=tenosynovial giant cell tumor; W=week; w/in=within.

^a EOT assessments do not need to be repeated if the assessment was done within the previous 7 days.

^b The Safety Follow-up Visit should be conducted 30 days (±5 days) after the last dose of study drug or prior to the initiation of any new TGCT therapy and/or surgery, whichever comes first. If a participant has been off study drug for more than 30 days at the time of decision to stop treatment, then the Safety Follow-up Visit will be conducted at the EOT visit. Information about new TGCT therapy and/or surgery will be collected during Safety Follow-up.

^c Disease follow-up will begin 12 weeks (±4 weeks) after last dose of study drug and an MRI will be required at this visit. All subsequent disease follow-up will be conducted by telephone every 16 weeks (±4 weeks) and a review of the participant's medical records for disease status changes will be performed. Disease follow-up will continue for up to 2 years after last dose of study drug, or until disease progression, withdrawal of consent, or start of new TGCT therapy and/or surgery, whichever occurs first. Participants who discontinue study due to confirmed disease progression by IRR will not need to complete Disease Follow-up Visit. Any SAE occurring during this follow-up period must be reported if assessed as related to study drug by the Investigator.

visits, participants may dose at home.

- ^d For conduct of End of Part 1 visit assessments refer to Section 11.5.1. Assessments from End of Part 1 will serve as C1D1 crossover assessments for C1D1 CO (ie, baseline assessments) and C7D1 assessments for participants continuing on study drug in Part 2. Participants continuing to Part 2 (open
- label) should follow assessment schedule in Table 2 and Table 3, as applicable, after all required blinded assessments are completed.
- ^e Histological confirmation of TGCT diagnosis is required for eligibility. Refer to Section 11.9.2 for more information.

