6.2. Endpoints

Primary Endpoint:

• Objective response rate (ORR, including complete response [CR] and PR) per RECIST v1.1 at Week 25

Key Secondary Endpoints:

- ORR per TVS at Week 25
- Change from baseline in active ROM of the affected joint, relative to a reference standard, at Week 25
- Change from baseline in the Patient-reported Outcomes Measurement Information System (PROMIS) physical function score at Week 25
- Change from baseline in the Worst Stiffness numeric rating scale (NRS) score at Week 25
- Change from baseline in EQ-VAS (EuroQol Visual Analogue Scale) at Week 25

• Response of at least a 30% improvement in the mean Brief Pain Inventory (BPI) Worst Pain NRS score without a 30% or greater increase in narcotic analgesic use at Week 25

Other Secondary Endpoints:

- ORR per RECIST v1.1
- ORR assessed by mRECIST at Week 25
- Duration of response (DOR; time from first PR or CR to disease progression or death) assessed using RECIST v1.1, TVS, and mRECIST
- Incidence of treatment-emergent adverse events (TEAEs), treatment-emergent serious adverse events, related TEAEs, dose reductions, dose interruptions, and discontinuation of study drug due to adverse event
- Changes from baseline in laboratory parameters, electrocardiograms (ECGs), and vital signs

Exploratory Endpoints:

Pharmacokinetics

• Correlation of PK with efficacy and/or safety

Pharmacodynamics

• Effects of pharmacodynamics in relation to safety or efficacy

Pharmacogenomics

• Germline polymorphisms in genes involved in the metabolism or disposition of vimseltinib or related to safety and/or efficacy

Efficacy and functional assessments

- ORR at Week 49
- Change from baseline in tissue damage score (TDS)
- Change from baseline in active ROM of the affected joint, relative to a reference standard, at Week 49
- Change from baseline in active ROM of the affected joint, relative to the contralateral joint, at Week 25
- Change from baseline in passive ROM of the affected joint, relative to a reference standard, at Week 25
- Change from baseline in passive ROM of the affected joint, relative to a contralateral joint, at Week 25
- Clinician Reported Outcome (ClinRO) and PRO assessments at Week 13 and Week 49
- Additional ClinRO and PRO assessments:

- Response of at least a 30% improvement in the mean BPI Average Pain NRS score without a 30% or greater increase in narcotic analgesic use at Week 25

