9.4.1. Blinding

In Part 1 of the study, the participants and all site personnel, including the Investigator, the site monitor, and the study team must be blinded to study drug treatment, with the exception of the following:

- Any site personnel for whom this information is important to ensure the safety of the participant in the event of a life-threatening medical emergency
- Any site personnel for whom this information is important to ensure the safety of the participant and their fetus in the event of a pregnancy
- Vendors responsible for pharmacovigilance and regulatory personnel at the Sponsor to satisfy serious adverse event (SAE) processing and reporting regulations
- Clinical supply chain personnel at the Sponsor and the vendor
- Unblinded statistician and programmer preparing the final (production) randomization list and unblinded analyses for the data monitoring committee (DMC)
- DMC
- Vendors analyzing PK and biomarker samples
- Vendor conducting the population PK analysis
- IRT vendor
- The Investigator, participant, site personnel, site monitor and study team will become unblinded to a specific participant's treatment assignment, if the participant has disease progression based on IRR or have reached Week 25 and completed End of Part 1 assessments.

9.4.2. Unblinding During Part 1

In exceptional circumstances, emergency unblinding is possible during Part 1 if, in the Investigator's opinion, immediate unblinding of the treatment is necessary for further management of the participant. Participants who are unblinded for emergency will be permanently discontinued from the study.

The Investigator is encouraged to contact the Sponsor or designee and discuss the participant's situation before making the decision to unblind.

Additionally, participants with disease progression confirmed by IRR before completion of Part 1 (ie, Week 25) will be unblinded. Additional information is provided in Section 10.5.

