9.6. Criteria for Dose Interruption and Modification

Study drug may be interrupted and/or modified at the discretion of the Investigator at any time due to AEs. Study drug may also be interrupted for other reasons in consultation with the Sponsor Medical Monitor. Any study drug interruption unrelated to an AE will be limited to 28 days. Upon resumption of study drug following a dose interruption, the Investigator must continue with the participant's original visit schedule calculated from Cycle 1 Day 1. Clinic visits and assessments should continue during dose interruptions.

Each

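### Lipase and amylase increases are the only two of the five Grade 3 or higher events in Section 5.2 with no scheduled measurement, so Part 1 yields no systematic data on them by arm (minor)

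*Protocol*

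**What the plan says.** **The signal.** Protocol Section 5.2 names five treatment-emergent events of Grade 3 or higher that occurred in more than one TGCT patient: CPK increased (29), AST increased (4), hypertension (4), and then "lipase increased 3 (3.4%), and amylase increased 3 (3.4"%).

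**What is measured.** The Part 1 schedule (Table 1) has rows for "Serum chemistry (central laboratory") and "Height (screening only), vital signs and weight". Table 14 sets the chemistry panel: 22 analytes, including CPK and AST but not lipase or amylase. Blood pressure is one of the vital signs. Section 11.9.14.2 also permits unscheduled local samples where there is a clinical reason. Section 11.9.14.3.8.1 makes an abnormal result an adverse event if the investigator judges it clinically significant.

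**What is analysed.** Section 6.2 has as a secondary endpoint "Changes from baseline in laboratory parameters, electrocardiograms (ECGs), and vital signs". SAP Section 9.11.3 lists 21 chemistry parameters for summary. Lipase, amylase and CPK are all absent from that list; CPK is named only for the listing, as an Amendment 3 addition. The same section plans change from baseline at scheduled visits and a shift table of baseline against worst later grade, both by treatment group. SAP Section 9.11.2 tabulates adverse events by preferred term and treatment group.

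**The concern.** Part 1 is the only placebo-controlled period, because placebo participants may cross over at Week 25. Section 12.1 gives detection of rare safety events as one basis for the sample size. The sponsor's own earlier data flag two laboratory events that the Part 1 panel does not measure, although a suitable blood sample is drawn at every main visit.

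A rise in enzyme level is found only by testing. Without scheduled tests, a low or zero count of either term in Part 1 would say little about whether the Phase 1/2 signal is real. Without a baseline, a rise already present at entry could not be told from one arising on treatment.

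**Working it through.** **1. Reproduce the Section 5.2 figures.** The section gives counts and percentages but no denominator. Seek one N for which 29/N, 4/N and 3/N round to 33.3%, 4.6% and 3.4%. Only N = 87 fits all: 29/87 = 33.3%, 4/87 = 4.6%, 3/87 = 3.4%.

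**2. Match the five events to the Part 1 schedule.** Central chemistry is drawn at screening, C1D1 (not repeated if the screening labs fell within 3 days), C1D15, Day 1 of Cycles 2 to 6 (five visits) and Week 25: 1 + 1 + 1 + 5 + 1 = up to 9. Vital signs are taken at the same 9 visits.

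| Event | Phase 1/2, Grade 3 or higher | Scheduled Part 1 measurements | In SAP 9.11.3 summary list |
|---|---|---|---|
| CPK | 29/87 | up to 9 (Amendment 3) | no (listing only) |
| AST | 4/87 | up to 9 | yes |
| Hypertension | 4/87 | 9 (blood pressure) | not applicable (vital signs, SAP 9.11.5) |
| Lipase | 3/87 | 0 | no |
| Amylase | 3/87 | 0 | no |

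The enzymes are missing from both the protocol table and the SAP table, so their absence is not a fault of text extraction.

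**3. Could rarity explain the difference?** Clopper-Pearson 95% limits for k of n are Beta(0.025; k, n−k+1) and Beta(0.975; k+1, n−k).
- 3/87: 0.7% to 9.7%.
- 4/87: 1.3% to 11.4%.

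The difference from AST and hypertension is one patient, so the enzymes were not materially rarer than either.

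**4. Cases at stake if the rate carried over (an assumption).** 80 × 3/87 = 2.76 vimseltinib participants per enzyme. Over the interval, 80 × 0.0072 = 0.6 to 80 × 0.0975 = 7.8. The chance of at least one is 1 − (84/87)^80 = 94%.

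**5. What complete testing could show.**
- With 0 of 80, the one-sided 95% upper limit is 1 − 0.05^(1/80) = 3.7%, still above 3/87 = 3.4%. At a true 3/87, the chance of 0 of 80 is 1 − 0.94 = 6%.
- Two-sided Fisher test, 80 against 40, with 0 of 40 on placebo: 8/80 gives p = 0.051 and 9/80 gives p = 0.028, so at least 9 cases are needed.
- Exact power at 3/87 against 0 is 0.0018, about 0.2%.

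The gain is therefore descriptive: baseline values, change by visit and shifts of any grade.

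**The case against.** The best reply is that no commitment is broken. Section 5.2 promises monitoring of safety laboratory values and the endpoint refers to laboratory parameters; neither names an analyte. CPK was added to the panel in Amendment 3, the version whose Section 5.2 prints the enzyme counts. The sponsor thus added the event seen in 33.3% of patients and not those seen in 3.4%. The reason may be in the Investigator's Brochure or in Section 9.6.1, whose text is not available. This stands: it is a choice of panel, and a reader who infers a contradiction or an error goes further than the documents allow.

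Four other stronger readings also fail.
- *The events will go unreported.* An abnormal result that needs further testing, intervention or a dose change counts as clinically significant and becomes an adverse event, tabulated by arm. What is lost is mainly symptom-free change.
- *The results will favour vimseltinib.* In Part 1 participants and site personnel, and also "the site monitor, and the study team must be blinded to study drug treatment", apart from listed exceptions. Under-ascertainment is therefore expected in both arms, not in one.
- *Nobody could know how many participants were tested.* SAP Section 9.11 expects some local results in the data, and Sections 8.3 and 8.4.1 handle unscheduled ones. The documents do not say whether local enzyme results are entered, so this number may or may not be recoverable.
- *The other three events are fully covered.* That is true of scheduled measurement only. CPK, about ten times as frequent, is missing from the SAP summary list too.

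It is also fair to say that the remedy cannot rule out the Phase 1/2 rate, as step 5 of the working shows.

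**Conclusion.** The point holds as a minor, cheap improvement. Two of the five events have no scheduled measurement, so the planned change-from-baseline and shift outputs cannot include them, and adverse event counts for these terms are not incidence estimates. The size, about 2.8 participants per enzyme among 80, assumes that the Phase 1/2 rate carries over. That study pooled several dose cohorts and the exposure is not stated; the confidence interval does not cover either uncertainty. Nothing here affects the efficacy conclusions, and the documents do not support a formal safety test of these events.

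**What to change.** 1. At the next protocol amendment, and not in one opened for this alone, add lipase and amylase to the Chemistry column of Table 14, run on the central sample already drawn.
2. Add both, and CPK, to the parameters summarized in SAP Section 9.11.3, for participants with a baseline value. Placebo participants who have not yet reached Week 25 can use that visit as the crossover baseline: "Assessments from End of Part 1 will serve as C1D1 crossover assessments for C1D1 CO (ie, baseline assessments").
3. Keep the output descriptive, with no between-arm test.
4. Where measurement was not systematic, footnote the two terms in the safety tables: the counts are not incidence estimates and do not show absence of the signal. This needs no amendment.

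**Cost.** No extra visit or draw. At most 9 × 120 = 1,080 Part 1 chemistry samples, hence at most 2 × 1,080 = 2,160 added results. There is a small assay cost, and some symptom-free abnormal values and adverse event reports will need review. Tables 9 to 11 have no rule for these enzymes, but Section 9.6 already provides that "Study drug may be interrupted and/or modified at the discretion of the Investigator at any time due to AEs". Ethics and regulatory approval is needed ("Approximately 45 centers globally"), which is why the change should ride on another amendment. Enrollment status is not given; Amendment 3 is dated 31 May 2023 and the SAP 9 August 2023. If few participants remain to be dosed, the panel change adds little to the Part 1 comparison and the footnote is the part still worth having.
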